### 4.2.2 Secondary Endpoint

Secondary Effectiveness Endpoint: improvement in the appearance of any one or more measurement of photoaging damage (fine wrinkles, skin texture, dyschromia/pigment, skin radiance, pore size and overall appearance) by the investigator using the quartile improvement score comparing standard 2D baseline photograph and the 1 month post final treatment photograph. Reported percent change in improvement.

### 4.2.3 Safety Endpoints

Serious Adverse Events (SAEs) related and unrelated to the treatment procedure or to the CLEAR + BRILLIANT TOUCH® diode laser.

The severity of post-treatment skin responses:

- Immediate post-treatment erythema and edema (Visits: 1 and or 2 if screening and treatment on same day, Visits 3, 4 and 5)
- Prolonged post-treatment erythema, edema, dryness/flakiness, hypopigmentation, hyperpigmentation, blistering, scarring. (Visits 6 & 7)

The evaluation of pain and discomfort immediately after the treatment (within 60 minutes) as reported by the subject on a visual analog scale (VAS).

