	Secondary Effectiveness Endpoint: improvement in the appearance of at least one measurement of photoaging damage (fine wrinkles, skin texture, dyschromia/pigment, skin radiance, pore size and overall appearance) by the investigator using the quartile improvement score comparing standard 2D baseline photograph captured via Canfield VISIA CA system to 1 month post final treatment photograph. Reported percent change in improvement.			
	Safety:			
	
 
Serious Adverse Events (SAEs) related and unrelated to the treatment procedure or to the CLEAR + BRILLIANT TOUCH® diode laser system.
 
			
	
 
The severity of post-treatment skin responses:         
 
Immediate post-treatment erythema and edema.
 
Prolonged post-treatment erythema, edema, dryness/flakiness, hypopigmentation, hyperpigmentation, blistering, scarring.
 
 
 
The evaluation of pain and discomfort immediately after the treatment (within 60 minutes) as reported by the subject on a visual analog scale (VAS)
 
			

Protocol [V01-CBT-401] Bausch Health Americas, Inc.

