#### 6.5 Data Collection

Subject demographic information, procedural data, adverse events, treatment observations and study required assessments will be documented on the case report forms (CRFs). Study subjects will complete satisfaction and modified global aesthetic improvement scale evaluations at the 3-month follow up. The Investigators will assess post treatment skin effects immediately post treatment, at follow up visits (prolonged post treatment) and quartile improvement scores at one (1) month and three (3) months in comparison to baseline photography. Blinded Investigators will provide analysis of unmarked 2D photo sets via Canfield clinical system. Reviewers will select the order of baseline and post treatment at one (1) month and three (3) months. Then based on their selection assess photos for

percentage improvement in photoaging damage using the quartile improvement scale and score 0-4.

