#### 6.8 Schedule of Events Table

	VISIT 1	VISIT 2	VISIT 2a	VISIT 3	VISIT 4	VISIT 5	VISIT 6	VISIT 7
PROCEDURES	Screening Visit (Day -30 to 0)	Treatment #1 (Baseline)	Day 14 Biopsy (14 days post treatment #1, +/- 7 days)	Treatment #2 (1-month post treatment #1, +/- 7 days)	Treatment #3 (1-month post treatment #2, +/- 7 days)	Treatment #4 (1-month post treatment #3, +/- 7 days)	1-Month F/U (1 month post final treatment, +/- 7 days)	3-Month F/U (3 months post final treatment, +/- 7 days)
Informed Consent/Photo	X							
Release								
Demographics	X							
Medical History	X	X						
Vital Signs	X							
Concomitant Medications	X	X		X	X	X	Х	X
Inclusion/Exclusion Criteria	Х	Х						
Previous Therapies	Х	Х						
Urine Pregnancy Test	X	X						
2D Standard Photography		X		X	Х	Х	X	Х
Investigator Intake Assessments	Х	X				, , , , , , , , , , , , , , , , , , ,	, A	
Punch Biopsy	X		X					X
Laser Treatment		X		X	Х	Х		
VAS Visual Analog Scale		X		X	X	X		
Side Effects Evaluation		X		X	X	X	Х	Х
Adverse Events Review	Х	X		X	X	X	X	X
Investigator Quartile Improvement Evaluation							X	X
Prolonged Treatment Effects							Х	Х
Subject GAIS								Х
Subject Diary a		X		X	Х	Х		
Subject Satisfaction		,				,		Х
End of Treatment(s)						Х	1	,,
- · · · · · · · · · · · · · · · · ·		1			1	, ,	1	

<sup>a. Subject's will log post-treatment skin responses, side effects (e.g., erythema, edema) using a scale of 0 to 3 (none to marked) after each treatment for seven (7) days in the subject diary.

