#### Visit 2a

Biopsy Patients Only (14 days post treatment #1, +/- 7 days)

Biopsy #2 of selected five patients

#### Visit 3

Treatment #2

(one-month post treatment #1, +/- 7 days)

This treatment visit will include:

- Prior to treatment: wait at least 15 min indoors, 2D standard photography via Canfield VISIA CA
- · Laser treatment to the face
- VAS Scale
- Post Treatment Skin effects (provider)
- Review for Adverse Events (provider)
- Subject Diary post treatment (7 days) given to patient

#### Visit 4

Treatment #3 (one -month post treatment #2, +/- 7 days)

This treatment visit will include:

- Prior to treatment: wait at least 15 min indoors, 2D standard photography via Canfield VISIA CA
- Laser treatment to the face
- VAS Scale
- Post Treatment Skin effects (provider)
- Review for Adverse Events (provider)
- Subject Diary post treatment (7 days) given to patient

#### Visit 5

Treatment #4 (one-month post treatment #3,+/- 7 days,)

This treatment visit will include:

• Prior to treatment: wait at least 15 min indoors, 2D standard photography via Canfield VISIA CA

Page 24 of 49

- Laser treatment to the face
- VAS Scale
- Post Treatment Skin effects (provider)
- Review for Adverse Events (provider)
- Subject Diary post treatment (7 days) given to patient

#### Visit 6

Follow-Up Visit (one-month post treatment #4, +/- 7 days)

This follow-up examination will include:

- Photography: wait at least 15 min indoors, 2D standard photography via Canfield VISIA CA
- Prolonged Post Treatment Skin effects
- Review for Adverse Events
- Investigator Quartile Percent Improvement Evaluation

#### Visit 7

Follow-Up Visit (three months post treatment #4, +/- 7 days)

This follow-up examination will include:

- Photography: wait at least 15 min indoors, 2D standard photography via Canfield VISIA CA
- Prolonged Post Treatment Skin effects
- Review for Adverse Events
- Subject GAIS and satisfaction
- Investigator Quartile Percent Improvement Evaluation
- Biopsy #3 of selected five patients

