### 8. ASSESSMENT OF SAFETY

### 8.1 Specification of Safety Parameters

- Post-treatment skin responses, side effects (e.g., erythema, edema) will be scored by the study investigators, as appropriate, using a scale of 0 to 3 (none to marked), immediately after treatment, for each treatment.
- Side effects (prolonged erythema, edema, skin darkening or lightening in the treatment area, scarring, dryness/flakiness, blistering) will be scored, using a scale of 0 to 3 (none to marked), by study investigators at the beginning of every subsequent treatment, and at all follow-up visits.
- Subject's will log post-treatment skin responses, side effects (e.g., erythema, edema) using a scale of 0 to 3 (none to marked), after each treatment for seven (7) days in the patient diary.
- In addition, study subjects will be instructed to report all complications experienced post study procedure to the site personnel as soon as they occur/are observed.
- It is the Investigator's responsibility to determine seriousness, severity, and relatedness of the Adverse Event to the device and the procedure using the definitions below.

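### The protocol conflicts with itself on which visits count for prolonged skin responses and on when adverse event recording starts, so some non-serious events fall outside the safety results

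*Combined protocol and SAP*

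**What the plan says.** **Prolonged skin responses.** The endpoint in section 4.2.3 reads "Prolonged post-treatment erythema, edema, dryness/flakiness, hypopigmentation, hyperpigmentation, blistering, scarring. (Visits 6 & 7". Section 6.5 says the investigators will "assess post treatment skin effects immediately post treatment, at follow up visits (prolonged post treatment", which also ties the prolonged assessment to follow-up. In the section 6.8 schedule the row "Prolonged Treatment Effects" is marked at Visits 6 and 7 only. Section 8.1 differs: the same kinds of response are scored from 0 to 3 "by study investigators at the beginning of every subsequent treatment, and at all follow-up visits". The synopsis lists "Prolonged post-treatment erythema, edema, dryness/flakiness, hypopigmentation, hyperpigmentation, blistering, scarring" and names no visits.

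Two other places bear on this. The schedule row "Side Effects Evaluation" is marked at Visits 2 to 7 but does not say whether it means immediate or prolonged effects. The written lists for Visits 3, 4 and 5 carry one skin item, "Post Treatment Skin effects (provider", placed after the laser treatment and the pain scale.

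**AE recording.** Section 8.2 starts recording at the first exposure to the study product and ends it at the last follow-up visit. The schedule row "Adverse Events Review" is marked at Visit 1, before any exposure, and is not marked at Visit 2a. The written list for Visit 1 contains no AE review. Section 6.5.2 places biopsy #1 at screening, before Treatment #1.

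**Analysis.** Section 10.2 names SAEs, tolerability parameters (not defined) and VAS pain. It names no summary of other AEs, although sections 8.2 to 8.4 have all AEs recorded and classified by severity and relatedness.

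**The concern.** Safety is half of the stated objective, and the treatment is a course of four sessions. Skin harm can follow any of them, and section 9.2.2 lists discoloration, including temporary colour change, and scarring among the possible complications. If the endpoint looks only at Visits 6 and 7, harm that follows an earlier session and clears in between does not enter it. Two statisticians working from this document could produce different safety tables, one from 4.2.3 and one from 8.1.

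The AE start point raises the same kind of problem on a smaller scale. Biopsy #1 is a study procedure, and section 9.2.3 gives its risks as infection and a scar that may be permanent. It takes place before the recording window in 8.2 opens. A biopsied person who then leaves by choice before Treatment #1 is a screen failure (5.7), was never enrolled (5.6), and lies outside the ITT population that 10.1 makes primary for all analyses.

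**Working it through.** The plan gives no figure to reproduce here. The check sets the sections side by side and counts visits.

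**Step 1: visits at which prolonged responses count.**

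| Source | Visits | Scorings per subject |
|---|---|---|
| 4.2.3 endpoint | 6, 7 | 2 |
| 6.5 | follow-up visits (6, 7) | 2 |
| 6.8, prolonged-effects row | 6, 7 | 2 |
| 8.1 | 3, 4, 5 (before laser), 6, 7 | 3 + 2 = 5 |
| Synopsis | none named | not stated |

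At the maximum enrolment of 30, the endpoint wording admits 2 × 30 = 60 scorings and section 8.1 calls for 5 × 30 = 150. The difference is 3 × 30 = 90. With the 25 subjects used for power in 10.1, the counts are 50 and 125.

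**Step 2: how long an event has to disappear.** Treatments are one month apart, and Visit 6 is one month after Treatment #4. The nominal gap to the first endpoint look is 3 + 1 = 4 months from Treatment #1, 2 + 1 = 3 months from Treatment #2 and 1 + 1 = 2 months from Treatment #3, before the 7-day visit windows are applied.

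**Step 3: whether another scored record fills the gap.** For Visits 3 to 5, section 4.2.3 takes only immediate erythema and edema. The home diary (Appendix F) runs for seven days after each treatment and asks about erythema, edema and heat sensation. Neither covers pigment change, blistering or scarring. AE review at Visits 3 to 5 could catch such an event, but it would then be a non-serious AE, for which 10.2 names no summary.

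**Step 4: who is affected by the AE start point.**
- Only biopsy subjects have a study biopsy before first exposure, and there are at most five (7.3).
- Screening may be up to 30 days before Treatment #1 (6.8). For subjects without biopsy, the two may fall on the same day.
- Biopsy #2 at Visit 2a comes after Treatment #1, so it lies inside the 8.2 window. What is missing there is only the mark for AE review.
- SAEs fall under the separate rule in 8.1.1, which covers the study period and does not refer to exposure.

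**The case against.** The strongest reply on the skin responses is that collection and endpoint are different things. Section 8.1 uses the term side effects for the prolonged list, so the row "Side Effects Evaluation" at Visits 2 to 7 may well hold the pre-laser scores, and 10.2.1 summarises tolerability at every applicable time point. An endpoint that uses two visits out of a wider collection is a legitimate choice. The visit lists are weak evidence, since they also omit concomitant medications, which the schedule marks at Visits 3 to 5. Photographs are taken before each treatment, and the advice in 9.2.2 about persistent erythema implies a look at the skin before the laser is used again.

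Much of this stands, and it limits the point. It does not remove it. No section says that the row holds the 8.1 scores, section 8.1 also uses side effects for immediate responses, and the endpoint wording excludes the Visit 3-5 scores wherever they are kept.

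On AEs, section 8.1.2 is a definition and not a recording window. The statement in 8.2 that information is collected throughout the study need not conflict with a start at Treatment #1, since enrolment begins there. The principal investigator judges biopsy sites healed before Treatments #1 and #2 are scheduled (6.5.2), subjects are told to report complications at once (8.1), and Visit 3 brings an AE review soon after Visit 2a. These safeguards reduce the practical effect. The mismatch between 8.2 and the Visit 1 mark in the schedule remains.

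On the analysis, all AEs are recorded and graded, raw data go to the sponsor, and nothing confines the study report to the summaries in 10.2. Discoloration, prolonged redness and scarring are also scored skin responses. The gap is in planned presentation, which is why this part is secondary.

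**Conclusion.** The point holds as a conflict to reconcile. The safety endpoint as worded admits 2 of the 5 scorings per subject that section 8.1 requires, and so leaves out a pigment change, blister or scar that follows Treatments #1 to #3 and resolves before Visit 6. The AE start point in 8.2 conflicts with the schedule and leaves out non-serious complications of biopsy #1. The missing AE summary and the undefined tolerability parameters are an omission that would carry little weight alone.

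Three stronger readings are tempting, and the documents do not support them:
- A reader might infer that 90 of 150 scorings are lost. The count describes endpoint wording. The scores may be collected under another row.
- A reader might take five of 30 as the share of subjects affected by the AE start point. Five is a ceiling on those with an early biopsy. The gap falls mainly on a biopsied person who leaves untreated, and such a person is not enrolled and so is not among the 30.
- A reader might argue that SAE counts are uninformative in so small a trial and that this measures the harm of having no AE table. The documents give no SAE or AE rate, and the precision of an SAE count in 30 subjects would be the same with the table added.

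The counts assume full enrolment and attendance at every visit. No sample size, power or alpha figure changes, and SAE reporting is unaffected.

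**What to change.** 1. Reconcile 4.2.3, 6.5, the 6.8 schedule and the Visit 3-5 lists with 8.1, and state which schedule row holds the pre-laser scores. Report prolonged responses by visit for Visits 3 to 7. Visits 6 and 7 can stay as the post-course result.
2. Give 8.2 one start point for AE recording: the first study-specific procedure, including biopsy #1. Align the Visit 1 list with the schedule and mark AE review at Visit 2a. Add a listing of AEs in biopsied subjects who are never treated, since 5.7 and 10.1 keep them out of the ITT tables.
3. In 10.2, define tolerability parameters. Add counts and percentages of subjects with any AE and with device- or procedure-related AEs, by severity.

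The cost is some wording, one mark in the schedule, one listing and a few tables, mostly from data the protocol already collects. More AEs may be reported as a result. No visits are added.

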#### 4.2.4 Exploratory Endpoints

- i. Subject Modified Global Aesthetic Improvement Scale (GAIS) comparing their own photos at 3 months post treatments compared to baseline photos.
- ii. Subject Satisfaction with procedure recorded at 3 months post treatments.
- iii. Five (5) patients will have 2-mm punch biopsies from area of photoaging comparing baseline to 14 days and 3 months post treatments (location on face at discretion of investigating physician: either pre-auricular or at temple hairline. If face location is unattainable, the forearm, exposed to photoaging may be used as an alternate biopsy location). Pre- and post-treatment biopsies must be taken from the same general location for each patient.
- iv. Blinded Investigator: analysis of unmarked 2D photo sets via Canfield clinical system. Reviewers will select the order of baseline and post treatment onemonth photos. Then based on their selection assess photos for percentage improvement in photoaging damage using the quartile improvement scale and score 0-4. Reported percent change in improvement of correct order sets.
- v. Blinded Investigator: analysis of unmarked 2D photo sets via Canfield clinical system. Reviewers will select the order of baseline and post treatment three-months photos. Then based on their selection assess photos for percentage

improvement in photoaging damage using the quartile improvement scale and score 0-4. Reported percent change in improvement of correct order sets.

### 5. INVESTIGATOR SELECTION AND STUDY POPULATION:

### 5.1 Investigator Selection

Investigators will be qualified based on professional experience in the diagnosis and treatment of photoaged skin including fine and coarse wrinkles, dyspigmentation, loss of tone, texture and elastosis using energy-based devices including lasers.

Investigators should be familiar with the risks and benefits described in Section 9. Investigator training and experience will be determined by the Sponsor to be suitable based on the Investigator's medical training and licensure.

### 5.2 Number of Participants

Up to 30 subjects who meet all study/exclusion criteria will be considered for entry.

Application of the inclusion and exclusion criteria in the following sections will result in the selection of an investigational population which is approximately representative of the intended target population.

#### 5.3 Inclusion Criteria

Subjects must meet all the following inclusion criteria.

- 1. Male or female.
- 2. 18 to 65 years of age.
- 3. Written and oral informed consent must be obtained.
- 4. No more than Mild (I) to Moderate (II) classification on Glogau Photodamage Scale.
- 5. Fitzpatrick skin types I-VI.
- 6. Fitzpatrick wrinkle & elastosis scale class I-II, score 1-6 (fine wrinkles and mild elastosis).
- 7. Ability to read, understand and sign the informed consent form.
- 8. Agree not to take any new medications (unless prescribed by the study investigator) or undergo any other procedures that may potentially treat photodamaged skin (any other aesthetic treatments) during the study.

#### 5.4 Exclusion Criteria

Subjects will be excluded from the study if they meet any of the following criteria.

- 1. Pregnant, breastfeeding, or planning to become pregnant during the study.
- 2 History of any type of allergic reaction to lidocaine.
- 3. Recent and/or active localized or systemic infections.

- 4. Diagnosis/possibility of actinic keratosis, melasma, rosacea, or other significant skin conditions (e.g. skin cancer, active infections, cold sores, open wounds, rashes, burns, inflammation eczema, psoriasis).
- 5. Predisposition to keloid formation or excessive scarring.
- 6. Diagnosis of a condition that may compromise the immune system, such as: HIV, lupus, scleroderma, and/or systemic infections.
- 7. Known sensitivity to light or photosensitizing agents/medications are being taken.
- 8. Systemic steroids (e.g. prednisone, dexamethasone), which should be rigorously avoided prior to and throughout course of the treatment.
- 9. Use of retinoids less than 2 weeks prior to or during the study to completion.
- 10. Individuals undergoing Accutane™ treatment or drugs in a similar class.
- 11. Having skin that is still recovering from a cosmetic procedure: such as a chemical peel, or mechanical peel, or laser resurfacing within the previous 6 months.
- 12. Having had Botox injections, neurotoxin injections, or dermal fillers (such as collagen) within the past four months.
- 13. Sunburn and/or recent sun exposure on the treatment area in the last 2 weeks.
- 14. Subjects must agree to seek the advice of their medical doctor regarding any known or suspicious skin condition before laser treatment.
- 15. Any condition or situation that would prevent the subject from safely completing all protocol requirements for participation.
- 16. Subjects who are unable to communicate or cooperate with the investigator due to language problems, poor mental development, or impaired cerebral function.

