### 4. STUDY DESIGN AND ENDPOINTS

#### 4.1 Description of Study Design:

This is a prospective, non-randomized study of up to 30 subjects designed to assess the safety and effectiveness of a non-ablative fractional combination laser wavelength procedure for general resurfacing of photoaged skin. All study subjects will be treated on the whole face with the with the CLEAR + BRILLIANT TOUCH® diode laser 1927-nm & 1440-nm handpieces. Subjects will be treated with a consecutive series of four (4) treatments spaced 1-month apart, along with follow-up study visits at one (1) and three (3) months after final treatment. As primary and secondary effectiveness endpoints aim to evaluate improvement in photoaging damage post-treatment as compared to baseline following treatment with the FDA-cleared CLEAR + BRILLIANT TOUCH® System, no control group will be utilized.

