### 6.3 Study Procedure

[figure not shown]
During the study procedure, subjects will be treated with the CLEAR + BRILLIANT TOUCH® diode laser device combination wavelength 1440-nm and 1927-nm treatment.

Perform pattern preview test prior to use of device.

- 1. First the face will be cleansed with alcohol, topical anesthetic of 7% Lidocaine/7% Tetracaine will be applied 30 minutes prior to treatment.
- 2. Prior to treatment, the anesthetic will be fully wiped off and then face is cleaned again with rubbing alcohol to ensure face is free of all moisture and water. Allow to dry.
- 3. Provide patient protective eyewear. (Disposable or Non-disposable laser eye shields). Laser goggles for staff. With appropriate protection range for the system laser wavelengths (1440 nm  $\pm$  20 nm and 1927  $\pm$  20 nm) and optical density of 5 or greater.
- 4. Attach single-use treatment tip.
- 5. Pre-set for 3200 cm^2 treatment area coverage or Time: 40 minutes.
- 6. Full face will be treated with 4 passes of the 1440-nm Original handpiece on high setting for all skin types I-VI, with two passes in the horizontal direction and two passes in the vertical direction (Fig A.) in each treatment zone (Fig B, C). (Adjustments may be made to lower setting for patient tolerance)

7. Full face will be treated with 4 passes of the 1927-nm Perméa on high setting for all skin types I-VI, with two passes in the horizontal direction and two passes in

- the vertical direction in each treatment zone. (Adjustments may be made to lower setting for patient tolerance)
- 8. The total is a combined 8 passes in each treatment zone.
- 9. CeraVe® moisturizer and SPF 30+ to be applied to entire face immediately after treatment.

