### 7.3 Punch Biopsies

Up to five (5) subjects will be consented to provide skin biopsies. Each subject will provide up to three (3) punch biopsies. 2 mm punch biopsies will be taken from the location on the face in an area of photoaging at discretion of investigating physician either pre-auricular or at temple hairline. If face location is unattainable the forearm (exposed to photoaging) may be used as an alternate biopsy location and will receive the combined laser treatment in addition to receiving a facial treatment. Pre- and post-treatment biopsies must be taken from the same general location for each patient.

[figure not shown]
Biopsies will be obtained using standard sterile technique after an intradermal local anesthesia, closed with suture (at the discretion of the Sub-Investigator/Study Physician), and treated with topical antibiotic and sterile dressing in routine fashion. Subjects' skin may be marked with a surgical marker to use as reference. Complete anesthesia of the biopsy site will be confirmed prior to the punch being inserted.

The biopsies will be immediately transferred into 10% formalin solution and stored at room temperature. Collected biopsy samples will be sent to Propath for biopsy sample analysis. IHC staining for Procollagen I, elastin, CD31, lymphocyte count, Masson's trichrome, GAG (Colloidal/Fe), and H&E, with images. 15 samples total will be collected (5 sets at baseline, day 14 and final visit).

The biopsy sample manifest will be sent to Propath and will contain the subject number, product information, total number of biopsies collected, and any other relevant information needed to identify the samples post-analysis.

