#### 9.2 Risks

#### 9.2.1 Expected Responses

Clinical studies have shown that CLEAR + BRILLIANT diode laser treatments have a demonstrated safety profile. There is a very low incidence of side effects and complications associated with treatment. Risks and discomforts for subjects who participate in this study are the same as for subjects undergoing any dermatological laser treatment. Eye injury due to use of the laser system is a risk to the subject and the operator. Appropriate eye protection will be used to minimize that risk. Mild to moderate local pain is a typical reaction to laser treatments. Topical anesthetic will be applied prior to laser treatments. Eye injuries may result from numbing cream getting into the eyes. Eyes will be covered with protective eyewear during treatment and should remain closed during the treatment.

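### The allergy exclusion names lidocaine only, while the anesthetic applied before laser treatment also contains tetracaine

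*Combined protocol and SAP*

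**What the plan says.** Section 5.4, exclusion 2, excludes anyone with a "History of any type of allergic reaction to lidocaine". It is the only eligibility criterion that deals with allergy to an anesthetic.

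Section 6.3, step 1, describes the preparation of the face: "topical anesthetic of 7% Lidocaine/7% Tetracaine will be applied 30 minutes prior to treatment". Section 9.2.1 restates this in general terms without naming the agent: "Topical anesthetic will be applied prior to laser treatments". Section 4.1 plans a "consecutive series of four (4) treatments spaced 1-month apart".

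Section 5.4, exclusion 15, is a general safety clause: "Any condition or situation that would prevent the subject from safely completing all protocol requirements for participation".

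For the biopsy subgroup of up to five subjects, section 7.3 says "Biopsies will be obtained using standard sterile technique after an intradermal local anesthesia". The agent is not named there.

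**The concern.** The sponsor has treated allergy to the anesthetic as a reason for exclusion in its own right, and in broad terms, since any type of reaction counts. The criterion covers one component of a two-component product. A person known to react to the other component meets no term of exclusion 2, although the standard procedure would expose that person to it.

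What is at stake is subject safety at screening. A criterion that names one agent may also lead staff to ask about that agent only. The point does not concern the estimation of the treatment effect.

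**Working it through.** The plan gives no figure on this point, so the check sets the sections side by side.

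1. **What is applied.** Section 6.3, step 1: two active components, lidocaine and tetracaine, each at 7%.
2. **What the allergy criterion names.** Section 5.4, exclusion 2: lidocaine.
3. **Difference.** 2 components applied − 1 named = 1 not named (tetracaine).
4. **Is tetracaine covered elsewhere by name?** No. It appears only in section 6.3. It is absent from the eligibility criteria (5.3, 5.4), the pre-procedure assessments (6.2), the schedule of events and visit lists (6.8), and the risk sections (9.2.1 to 9.2.3). The one risk that section 9.2.1 attaches to the numbing cream is eye injury.
5. **Is the anesthetic optional?** Section 6.3 states the step without exception, and section 9.2.1 does the same. Neither gives an option to omit or substitute it. The visit-by-visit lists in section 6.8 do not repeat the step, so its use at all four treatments is an inference from 6.3 and 9.2.1, though a natural one.
6. **Could the biopsy anesthetic explain the lidocaine-only wording?** Not on the text. Section 7.3 does not name the agent and concerns at most five subjects, whereas exclusion 2 applies to everyone. The only lidocaine product named in the documents is the combination in section 6.3.
7. **What else could catch the case?** Exclusion 15, on its plain wording, could cover a known tetracaine reaction, because the anesthetic is part of the procedure that the subject must complete safely. Medical history is recorded at Visits 1 and 2 (6.8), and eligibility is confirmed at both (5.6). None of these names anesthetic allergy, so each works only if the history comes up and the investigator connects it with step 1 of section 6.3.
8. **Effect on the analysis.** Section 10.1 bases power on 25 subjects and enrolls up to 30, a margin of 30 − 25 = 5. If 30 are enrolled, losing one or two subjects for this reason (an assumed number, since the documents give no rate) uses one or two of those five places. The analysis methods do not depend on the criterion.

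**The case against.** The strongest reply is that the exclusion list as a whole already covers the case. Exclusion 15 is mandatory where it applies. The study is at a single center, under an investigator chosen for experience with energy-based devices (5.1). History is taken twice before the first treatment. Section 5.9.1 also requires discontinuation when an exclusion is recognized late, or when an adverse event makes continuing contrary to the subject's interest, which limits repeat exposure. On this view the two sections do not conflict: exclusion 2 never claims to list every component, and a subject can satisfy both as written.

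Most of this stands, and it sets the limits of the point. It does not remove the mismatch. The plan chose to name anesthetic allergy rather than leave it to the general clause, and then named one component of two. The late-recognition rule in section 5.9.1 refers back to the same exclusion list, so for tetracaine it again relies on exclusion 15.

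Four stronger readings are tempting, and the documents do not support them:

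- A reader might infer that a subject with a known tetracaine reaction must be enrolled. Exclusion 15 permits exclusion.
- A reader might infer that screening never asks about such reactions. The case report form is not among the documents. All that can be said is that the protocol text lists no such question.
- A reader might take 30 subjects × 4 treatments = 120 applications as the size of the problem. That is the maximum planned exposure of all subjects, not the number at risk.
- A reader might infer that anesthetic reactions would distort the skin-response data. The documents give no rate for this, and a reaction in a subject with no known history would raise the same question whatever exclusion 2 says.

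**Conclusion.** The mismatch is real and minor. Exclusion 2 does not name one of the two active components that section 6.3 applies. A subject with a known reaction to that component alone is kept out only by investigator judgement under exclusion 15.

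The number affected cannot be derived from the documents. That it is very small is a judgement, not a figure from the plan. Power and the primary analysis are not materially affected. The conclusion rests on the protocol text alone; a drug-allergy question on the case report form would narrow the gap in practice but would leave the criterion and the procedure out of step.

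**What to change.** Reconcile section 5.4, exclusion 2, with section 6.3, step 1, so that the allergy criterion and the screening history refer to the same components as the anesthetic applied. The clinical wording is for the sponsor and the investigator to decide, and none is proposed here.

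The cost is about one line in the protocol, plus one item on the screening form if it does not already ask the question. If the protocol has already been approved, section 13.2 requires review by the institutional review board before the change takes effect. The effect on recruitment should be negligible, on the same assumption that few people are affected. No change to the sample size or the analysis is needed.
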